A minimum of 93 participants (31 participants per group) aged 4-to-13 will be recruited through convenience sampling, consented, and randomized by staff to one-of-three preparation programs (VR, mock MRI, or booklet). Details of the comparison groups are outlined in **Table 4**. Given the restricted availability of the simulator, child life specialists, and the availability of participants, we are unable to fully randomly allocate participants. As such, participants will be randomly assigned to the intervention options available according to their individual availability (using Research Randomizer <https://www.randomizer.org/>). For example, if a participant is available on a Thursday that virtual reality and booklet are available, they will be randomly allocated to one of these interventions.

This phase will have open recruitment to all children and adolescents interested in participating, such that participants may not be BCCH patients scheduled for an MRI. This recruitment strategy was selected due to the resource constraints associated with limiting the evaluation group to MRI patients only.

Table 4. Details of the comparison groups.

	VR Simulation	MRI Preparation Booklet	Mock MRI
Facilitator	Research Assistant	Research Assistant	Child Life Specialist
Location	BCCH	BCCH	Simulation Room
Content	Refer to The Virtual Reality Simulation	Refer to MRI Preparation Book	Individualized intervention in physical simulator.

The different interventions will be held in separate private rooms located in BCCH, such that the VR and booklet groups will not have prior exposure to the imaging centre or the simulation room in advance of their assessment. This is to simulate our intended delivery in hospital, medical office, or clinic settings but minimize alternative explanations associated with testing in the simulation room where assessments will take place (previously described in **Table 3**).

Data will be collected throughout the implementation process (**Figure 3**). The predictive variables (demographics and relevant history, and delivery type) will be captured at the start of the session. The primary outcome variable is likelihood of success (pass/fail) of the MRI simulation, and will be measured at the end of the assessment. Anxiety will also be measured at three time points. Usability testing will be conducted throughout to capture possible quality improvements and amendments to each of the program delivery modes.

Inclusion/Exclusion Criteria

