Measure	Immediate Outputs	Intended Outcome
Primary		
MoTrak®	# of participants "prepared" to be scheduled for an effective MRI	
Improve access to MRI preparation for children who:
 
 - Live out of town - Would like to practice skills at home - Have mobility issues 
Improve non-sedation rates for MRI scans.

Venham Pictoral Test & Short STAI	# of participants with reduced anxiety # of parents with reduced anxiety	
Improve access to MRI preparation materials.
 
Improve behavioral compliance during medical procedures.

Secondary		
Smileyometer	# of participants who find the delivery mode fun and engaging to use	
Improve acceptability of preparation materials.
 
Improve satisfaction.

USE Questionnaire	# of parents who find the preparation materials useful	
Improve acceptability of preparation materials.
 
Improve satisfaction.

Natural Choice Selection	# of participants who select the booklet # of participants who select the mock MRI # of participants who select virtual reality # of participants who select none	Identify preference for engaging. Identify frequency of contact and time engaging.
Length of Stay	Minutes spent per segment	Improve hospital efficiency
Guided Survey	# of participants who find the booklet fun, easy to use, and good for learning about the MRI experience # of participants who find the mock MRI fun, easy of use, and good for learning about the MRI experience # of participants who find the virtual reality game fun, easy of use, and good for learning about the MRI experience	Improve utility of MRI preparation materials. Identify frequency of contact and time engaging.
Interpupillary Distance	Average interpupillary distance per age	Improve headset configuration.

Primary Measures

Predictive Success in Avoiding Sedation

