The predictive success in avoiding sedation will be measured using Motrak® software assessment. MoTrak® uses a sensor attached to the participant's head to determine the position of the head in space relative to a transmitter located within the simulator. The sensor records angular rotations as well as positional displacements from an initially calibrated position. This information is displayed and logged by the program in real-time, allowing objective observation of head motion in an MRI simulator.³² The fail threshold is set at 3mm of movement in any of the positional displacements (x,y,z), which is in accordance with imaging protocols at the Hospital.

Child Anxiety: Venham Picture Test – 5 minutes

Anxiety assessment with children will be completed in pictorial form to better adapt to the cognitive and communicative abilities and styles of younger children. The Venham Picture Test has been well-validated in children for assessing procedural anxiety^{33,34}, and comprises eight cards which two figures on each card, one anxious character and one non-anxious character. The children will be asked to point at the figure they feel most like at that moment. All cards will be shown in their number order. If the child points at the anxious figure, a score of one is recorded and if the child points at the non-anxious character, they will be given a score of zero. Children will complete the at three timepoints (before, during, after the mock MRI).

Secondary Measures

Parental Anxiety: Short State-Trait Anxiety Inventory (Short STAI) – 5 minutes

Anxiety assessment with parents/guardians and children at baseline, after completing the intervention, and before the mock MRI. The Short STAI is a 6-item, adapted version of the well-validated Spielberger State-Trait Anxiety Inventory Scale.³⁵ It distinguishes between general proneness to anxious behavior rooted in the personality and anxiety connected to a current state, and has been validated for use in children.³⁵

Demographics and Relevant History

Demographic and possible confounding information (age, sex, prior experience with medical imaging, experience with virtual reality, type of mobile phone) will be obtained through a data collection form. Data will be de-identified using a participant identification number.

Length of Stay (LoS)

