A priori power analysis was calculated using G-Power.³⁸ A total sample size (N) of 93 was calculated to be needed across the 3 groups (31 per group), with a significance level of 95% ($\alpha=0.05$) and a power of 90% ($\beta=0.10$), allowing for a 10% drop out rate. An effect size of 0.2 was selected to reflect the research suggesting that CLS preparation can reduce sedation rates by 20%.

Descriptive analysis will be conducted on the demographics and relevant history data.

Differences in predictive success of the MRI simulation ranking scores (pass or fail) will be examined using a Repeated Measures ANOVA, within-between interaction for three timepoint measurements (before, during, after) of anxiety and delivery type (VR, mock MRI, booklet). In the case of an off-normal distribution, non-parametric tests may be used. Multivariate analysis will test for possible confounding effects (demographics and relevant history).

Survey data (USE questionnaire, Smileyometer) will be analyzed using means and standard deviations of all respondents for each category of the questionnaires. The proportions of the participants reporting high, medium, or low levels will also be calculated.

Study staff will document responses to the guided survey and read the recorded answers back to participants to verify accuracy and elicit possible further reflection. All of the qualitative data will be uploaded to NVivo by study staff. When complete, study staff will code the information to identify major themes, gaps, barriers within the existing approach and the team will devise recommendations for improving the preparation programs. The phases of this process include:

- Familiarizing yourself with the data

- Generating initial codes
- Searching for themes
- Reviewing themes
- Defining and naming the themes
- Triangulation with other findings and producing a report

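### The pass/fail primary outcome is assigned to a repeated-measures test it cannot enter, and the stated 90% power is not tied to it or to any other outcome

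*Combined protocol and SAP*

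**What the plan says.** All of this is in section 4.4 (Phase 2).

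- **Primary outcome.** Before the eligibility criteria: "The primary outcome variable is likelihood of success (pass/fail) of the MRI simulation, and will be measured at the end of the assessment". Under Primary Measures: "The fail threshold is set at 3mm of movement in any of the positional displacements (x,y,z"). Each child therefore gives one yes/no reading.
- **Sample size.** Under Analysis and Interpretation: "A total sample size (N) of 93 was calculated to be needed across the 3 groups (31 per group"), with alpha 0.05, 90% power and a 10% dropout allowance. The rationale is: "An effect size of 0.2 was selected to reflect the research suggesting that CLS preparation can reduce sedation rates by 20" per cent. G*Power is named. The outcome, test family, effect-size metric, correlation between repeated readings and sphericity correction are not.
- **Analysis.** Same subsection: "Differences in predictive success of the MRI simulation ranking scores (pass or fail) will be examined using a Repeated Measures ANOVA, within-between interaction". The factors of that interaction are then given in the same sentence: "for three timepoint measurements (before, during, after) of anxiety and delivery type (VR, mock MRI, booklet"). Non-parametric tests are allowed if the distribution is not normal, and a multivariate analysis is to look at confounding.
- **Anxiety.** It is measured three times. The outcome table lists "Venham Pictoral Test & Short STAI" under Primary. The text that follows keeps the Venham test under Primary Measures but puts the Short STAI under Secondary Measures.

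Section 4.2 sets out hypothesis 2a (VR and booklet differ) and hypothesis 2b (VR and mock MRI do not differ).

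**The concern.** The analysis sentence takes its response from one outcome and its time factor from another. Only anxiety has three timepoints, so only anxiety can be the response in a group-by-time interaction. As written, the one sentence that assigns a test to the primary outcome variable cannot be carried out. A test would have to be chosen later, possibly with the data in view.

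The power statement has a related gap. Because 0.2 is justified by sedation rates, and pass/fail is this study's measure of predicted success in avoiding sedation, a reader will naturally take the 90% to cover pass/fail. Nothing in the plan shows that it does. If power for pass/fail is much lower, a non-significant VR-booklet comparison says little, and a non-significant VR-mock MRI comparison could be taken as support for hypothesis 2b when it is only imprecise. Phase 3 also carries the predicted non-sedation rates into its cost-effectiveness ratios.

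**Working it through.** **1. Can the stated 93 be reproduced?** Inputs from the plan: 3 groups, 3 timepoints, effect size 0.2, alpha 0.05, power 0.90, dropout 10%. Reading 0.2 as Cohen's f for a within-between interaction, with correlation ρ and sphericity factor ε (neither stated):

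λ = ε·f²·N·3/(1−ρ), df1 = 4ε, df2 = 2(N−3)ε.

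| ρ | ε | N for 90% power | in equal groups |
|---|---|---|---|
| 0.5 | 1 | 67 | 69 |
| 0.5 | 0.75 | 82 | 84 |
| 0.37 | 1 | 84 | 84 |
| 0.5 | 0.5 | 109 | 111 |

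For example, with ρ = 0.37, ε = 1 and N = 84: λ = 0.04 × 84 × 3/0.63 = 16.0, power 0.903. Adding dropout, 84/0.9 = 93.3 and 84 × 1.1 = 92.4, so about 93. The figure is compatible with an anxiety-type interaction, but only for particular unstated ρ and ε.

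**2. Does 0.2 give 93 for a single reading?** A chi-square test with w = 0.2 and 2 df needs N = 317; its power is 36% at N = 84 and 39% at N = 93. A one-way three-group ANOVA with f = 0.2 needs 321 in equal groups.

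**3. Illustrative power for pass/fail.** The plan gives no arm-specific pass rates, so every row below is an assumption. The 82% and 84.6% anchors come from Table 2 in section 3.0: 283/344 = 82.3% converted to non-sedated MRI, and (283 + 8)/344 = 84.6% passed the simulator. Those were referred patients prepared by Child Life Specialists; here "participants may not be BCCH patients scheduled for an MRI". The 20-point gap reads the cited 20% as absolute, which the plan does not say. Arms are taken as equal, from 28 (31 × 0.9 = 27.9) to 31. The test is the uncorrected Pearson test at two-sided 0.05 without multiplicity adjustment, with power by full binomial enumeration. In the three-group test, VR equals mock MRI and booklet is 20 points lower.

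| VR / booklet pass rate (%) | VR vs booklet | Three-group test |
|---|---|---|
| 60 / 40 | 31-37% | 33-35% |
| 82 / 62 | 39-42% | 41-45% |
| 84.6 / 64.6 | 41-45% | 44-48% |
| 95 / 75 | 60-65% | 63-69% |
| 100 / 80 (boundary) | 84-89% | 94-96% |

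Fisher's exact test is lower: 29-33% at 82/62. If the 20% is relative, power is 29-31% for 82% against 65.6% passing (82 × 0.8), and 7% for 18% against 22.5% failing (22.5 × 0.8 = 18).

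**4. Detectable gap and precision.** With VR at 82%, the VR-booklet gap giving 90% power is 40.6 points at 28 per arm and 38.4 at 31. The expected 95% CI half-width at 82/62 is 1.96·√[(0.82×0.18 + 0.62×0.38)/n] = 0.229 (n = 28) or 0.218 (n = 31). For VR against mock MRI, both at 82%, it is 1.96·√[(2×0.82×0.18)/n] = 0.201 or 0.191.

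**The case against.** The strongest reply is that the 90% was meant for anxiety. The Venham test is listed as primary in both the table and the text, a three-timepoint interaction suits it, and step 1 shows that 93 can be obtained that way. This stands as far as it goes. A reader might infer that 93 is a miscalculation; the documents do not support that. But the plan does not say the 90% belongs to anxiety, a sedation rate cannot justify an effect size on an anxiety scale, and pass/fail would still have neither a test nor a power statement.

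Second, a reader might infer that true power for pass/fail is about 40%, or that the 90% is false. Neither follows. The plan gives no pass rates for its arms, the anchors come from a different population, and a figure attached to no outcome is undefined rather than disproved. At the 100/100/80 boundary the three-group test exceeds 90%. The illustrations show only that, away from the boundary, a 20-point gap falls well short. The 93 is also a stated minimum, so the powers apply at that floor.

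Third, the plan allows non-parametric tests and a multivariate analysis. The first is conditional on non-normality and the second is for confounding; neither specifies a binary comparison of pass/fail.

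**Conclusion.** The point holds as a mismatch between outcome and test, together with a power statement attached to nothing. It is not an arithmetic error. That conclusion needs no assumed pass rate: one binary reading per child cannot be the response in a three-timepoint interaction, and no other test or power figure covers it.

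The size does rest on assumptions (a 20-point absolute gap, equal arms of 28 to 31, uncorrected Pearson test). Over the non-boundary pass rates in the table, power is 31-65% for VR against booklet and 33-69% for the three-group test. With VR at 82-85%, a true 20-point VR-booklet gap would be missed in about 55-61% of such trials (1 − 0.448 to 1 − 0.392). This must be corrected, because it concerns the outcome the plan itself calls primary.

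**What to change.** Keep 93 as the stated minimum and amend Analysis and Interpretation in section 4.4:

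1. Analyse pass/fail as a single binary outcome across the three groups. Report the VR-booklet and VR-mock MRI differences in pass proportion with 95% CIs. Add a binary regression model with the plan's confounders and the set of options available to each child at allocation, since allocation depends on availability. Apply the repeated-measures group-by-time interaction to the anxiety scores only.
2. State power for pass/fail separately, as a short table by assumed pass rates with the test named. Add the gap detectable with 90% power (about 38-41 points at an 82% anchor) and the expected CI half-width (about 22-23 points at 82/62).
3. Keep the 90% only if it is labelled with the anxiety scale it was calculated for, f = 0.2, and the correlation and ε used. Replace the sedation-rate rationale with one about that scale.
4. State that a non-significant pass-rate result, whether VR against booklet (2a) or VR against mock MRI (2b), will not be read as no difference.

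The cost is a less favourable stated power for pass/fail. No enrolment or data collection is added.

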The issue of pre-procedural anxiety is critically important because it not only impacts patient experience and is associated with psychological and physiological distress, but it can affect the efficiency of medical procedures, length of stay in the hospital (LoS), and resource utilization – all of which have economics impacts to both families and the health

system. During medical imaging procedures specifically, anxiety can cause non-compliance or unintentional movement which often leads to failure to complete the procedure or poor image quality, necessitating multiple attempts or the use of sedation to achieve the desired quality of imaging. The impact of sedating a patient has several downstream effects, including the increased potential for adverse events, as well as the need for specialized clinical staff (i.e. Anesthesiologists, Post-Anesthetic Care Nurses, etc.), medications, and lengthier post-procedural monitoring. Studies have also indicated an increase in negative post-procedural outcomes when patients are sedated, such as increased pain perception, increased pharmaceutical consumption, reductions in sleep and eating, generalized anxiety, and greater dissatisfaction.²⁻⁸

Child Life Magnetic Resonance Imaging (MRI) Simulations

The literature suggests that approximately 50-to-75% of all patients who undergo MRI exams at pediatric hospitals are sedated.⁹ CLS reduce sedation rates by exposing pediatric patients to MRI simulations, thus alleviating symptoms of pre-procedural anxiety and distress. MRI simulations include mock scans that appear and sound identical to the real MRI, but lack the magnet, and thus functionality to take images. It's suggested that preparation programs like this can reduce sedation rates by about 20% (those who are eligible, recruited, and successful).⁹

Between November 2017 and January 2019, approximately 377 of the pediatric patients attending BCCH for MRI were eligible and referred for preparation with a CLS. Of the patients who proceeded with simulation (N=344), 82% were able to successfully be converted to a non-sedated MRI (**Table 2**).

Table 2. Simulation statistics from BC Children's Hospital (BCCH) Child Life Department, Nov2017 – Jan2019.

	Non-Sedated MRI	Sedated MRI
Passed Simulator	283	8
Failed Simulator	0	53
TOTAL	283	61

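### The effect size of 0.2 behind N=93 is justified by a 20% fall in sedation, but it reproduces 93 only as Cohen's f for a group-by-time interaction, where it means a large anxiety difference

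*Combined protocol and SAP*

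**What the plan says.** The power paragraph in section 4.4 (Analysis and Interpretation) states: "A total sample size (N) of 93 was calculated to be needed across the 3 groups (31 per group"), with alpha 0.05, power 90%, and "allowing for a 10% drop out rate". It names G*Power as the software. The effect size is explained in one sentence: "An effect size of 0.2 was selected to reflect the research suggesting that CLS preparation can reduce sedation rates by 20" per cent.

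The 20% comes from section 3.0 (Child Life MRI Simulations), where preparation programmes of the mock-scan kind "can reduce sedation rates by about 20% (those who are eligible, recruited, and successful"). Whether this is an absolute or a relative reduction is not said.

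The only inferential test named in section 4.4 is a repeated-measures ANOVA, "within-between interaction for three timepoint measurements (before, during, after) of anxiety and delivery type". The primary outcome variable in the same section is pass or fail on the simulated MRI. The outcomes table in that section also lists the anxiety scales under its primary heading.

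The plan does not give the effect-size metric, the test used in the power run, the number of readings, the correlation between readings or the sphericity correction.

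**The concern.** Two quantities share the numeral 0.2 and little else. One is a change in the proportion of children sedated. The other, in the G*Power routine that matches the named test, is Cohen's f: the SD of the group-by-time interaction means divided by the SD of a single reading. The plan offers no conversion from one to the other.

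The 20% also belongs to a different comparison. It is the effect of having a preparation programme. This trial compares VR with a booklet, which is itself preparation, and with mock MRI, from which section 4.2 expects no difference.

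A reader will take 93 children as giving 90% power for a 20% fall in sedation. If they do not, a null result on anxiety or on pass/fail could be given more weight than the design supports.

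**Working it through.** **Inputs from section 4.4:** three equal arms, alpha 0.05, power 0.90, effect size 0.2, drop-out 10%, stated N 93. **Assumed, because not stated:** 0.2 is Cohen's f; correlation rho = 0.5 and epsilon = 1 (no sphericity correction) unless varied; m = number of readings.

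**1. Reproducing 93.** For the within-between interaction, noncentrality = N × m × f² × epsilon / (1 − rho), with degrees of freedom (k − 1)(m − 1)epsilon and (N − k)(m − 1)epsilon, and k = 3.

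| Readings | Settings | N needed | Equal arms | With drop-out |
|---|---|---|---|---|
| 2 | rho 0.5, epsilon 1 | 83 | 84 | 93 |
| 3 | rho 0.5, epsilon 1 | 67 | 69 | 77 |
| 3 | rho 0.5, epsilon 0.75 | 82 | 84 | 84/0.9 = 93.3 |
| 3 | rho 0.37, epsilon 1 | 84 | 84 | 84/0.9 = 93.3 |

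For two readings the noncentrality at N = 84 is 84 × 2 × 0.04 / 0.5 = 13.44, and power is 91%. Drop-out gives 83/0.9 = 92.2, or 84 × 1.1 = 92.4, both rounding up to 93. Per arm, 28 × 1.1 = 30.8, so 31.

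For three readings at the same defaults, N = 84 has noncentrality 84 × 3 × 0.04 / 0.5 = 20.16 and power 96%.

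Other meanings of 0.2 do not come near 93, even before drop-out: one-way ANOVA with f = 0.2 needs about 320 in total, and a chi-square test with w = 0.2 on 2 df needs 317.

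**2. What f = 0.2 means for anxiety.** Let d be the largest between-arm difference in change, in single-reading SDs. The interaction SD is d × √(mean square of the centred arm pattern × mean square of the centred time pattern). Set this equal to 0.2.

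- Two readings, one arm differs: √(2/9 × 1/4) = 0.2357, so d = 0.2/0.2357 = 0.85.
- Two readings, arms evenly graded: √(1/6 × 1/4) = 0.2041, so d = 0.98.
- Three readings, one arm differs by a step: √(2/9 × 2/9) = 0.2222, so d = 0.90.
- Three readings, arms evenly graded and linear over time: √(1/6 × 1/6) = 0.1667, so d = 1.20.

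Over all possible three-reading patterns the range is 0.73 to 1.20. These figures equal SDs of the change score only at rho = 0.5. For two readings they become 0.72-0.83 SDs of change at rho 0.3 and 1.10-1.27 at rho 0.7.

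**3. What 93 children give for pass/fail.** As an illustration, take 82% (283/344 in Table 2 of section 3.0) against 62%, reading the 20% as percentage points. Both rates are assumptions for this trial. Power = Φ[(0.20 − 1.96 × SE₀)/SE₁], with SE₀ = √(2 × 0.72 × 0.28/n) and SE₁ = √((0.82 × 0.18 + 0.62 × 0.38)/n).

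- n = 28: SE₀ = 0.1200, SE₁ = 0.1170; (0.20 − 0.2352)/0.1170 = −0.30; power 38%.
- n = 31: SE₀ = 0.1140, SE₁ = 0.1112; (0.20 − 0.2235)/0.1112 = −0.21; power 42%.

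For 90% power this comparison needs about 104 per arm before drop-out. Over several other assumed base rates with a 20-point gap, power at 28-31 per arm runs from about 33% to 50%. If the 20% is relative, the gap is under 20 points and power is lower at a given base rate.

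**The case against.** The plan never says which test was run in G*Power. The interaction test is inferred from the analysis paragraph and from working back to 93, and the settings cannot be identified uniquely: two readings at default values and three readings with other values both arrive there. That stands, and every SD figure here is conditional on it.

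A reader might infer that the plan fixes the detectable effect at 0.85-0.98 SD. The documents do not support this. That range is exact only for two readings, and the plan names three. Nor can 0.85 and 0.90 SD be joined under one claim of 90% power at 84 children: the first belongs to two readings, the second to three, and three readings at default settings give 96%. The correlation matters too. With two readings and N = 84, power at f = 0.2 is 78% at rho 0.3 and 99% at rho 0.7.

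It can also be said that sizing the trial on anxiety is legitimate, since the outcomes table lists anxiety under its primary heading. That is fair, and it is why 93 need not be discarded. It does not rescue the stated reason for 0.2, and it leaves the pass/fail outcome without a power figure.

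Finally, the 82% v 62% comparison is an illustration, and that a null result would be over-read is a prediction. Both points stand. The mismatch between a 20% change in a rate and f = 0.2 depends on neither.

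**Conclusion.** The stated basis for the effect size is wrong. Among the readings tried, 93 is recovered only with 0.2 as f in a repeated-measures interaction, and there it is not a 20% fall in sedation. The cited 20% is also not the effect of VR against booklet or mock MRI.

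On the inferred reading, the calculation targets a large anxiety difference that the plan does not justify, roughly 0.7 to 1.2 single-reading SDs depending on the number of readings and the pattern. It says nothing about pass/fail, where power is well below 90% for a 20-point gap under the base rates tried.

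A reader might go further and conclude that 93 is an arithmetic error or that the anxiety analysis is underpowered. Neither follows: 93 is reproducible, and three readings at default settings would need fewer children (67, about 77 with drop-out). What is wrong is the link between the number and its stated justification. The sentence should be corrected.

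**What to change.** Keep N = 93, and in section 4.4:

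1. Delete the link between 0.2 and a 20% reduction in sedation.
2. Name the effect-size metric and the test used, and give the settings actually entered: number of readings, correlation and sphericity correction.
3. If those settings confirm the interaction test, restate the power as 90% for the group-by-time anxiety interaction at f = 0.2, with the anxiety difference this implies and the SD in which it is expressed. Recompute it for the three readings to be analysed, since power or detectable difference will change if two were entered.
4. State separately the power that 93 children give for the pass/fail primary outcome, under declared assumptions about the pass rates.

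This is a text change with a short recalculation and no extra participants. The cost is that the stated detectable effect and the power for the primary outcome will look less favourable than the present wording suggests.
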